In total, 192 participants will be included in this study. This sample size was determined by a power analysis, detailed below in Statistical Analysis.

Inclusion criteria are:

- Pure-tone audiometry thresholds ≤80 dB HL at 500 Hz
- One year of age and older
- Normal candidacy requirements for cochlear implantation met
- No cochlear abnormality that might prevent full insertion of the CI electrode array
- No additional handicap that would prevent study procedures from being followed

Exclusion criteria are:

- Chronic otitis media
- Malformed cochlea
- Auditory neuropathy spectrum disorder (ANSD)
- Presence of ear tubes
- Prior middle ear surgeries or trauma including disruption of ossicles

At any point in the study, the participants are free to end their involvement without any effect on their clinical care. Because this study does not involve any changes to the CI, its use, or the surgical technique, if a participant were to elect to end involvement in the study, it does not impact their treatment in any way. CI candidates meeting inclusion criteria will be given the opportunity to participate at the time of their regular pre-operative clinic visit or on the day of surgery itself.

Randomization

Interested CI candidates meeting study inclusion criteria will be randomized to one of two treatment arms. Randomization has been accomplished using a “randomized block design” to ensure that equal numbers of participants are included in each “treatment condition.” For each participating institution, an impartially designed randomization schedule has been drawn up with the assistance of a biostatistician. The arm to which participants are randomized will be unknown to the investigators at the time of enrollment and to the participants themselves. By necessity, surgeons themselves will be “unblinded” on the day of surgery. Figure 1 depicts the study’s randomization arms and post-operative outcome measures.

Arm 1: Audible ECochG Response Off

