- a) Ensure that no cerumen or surgical preparation fluid is in the external ear canal. Place the ear piece in the external ear canal and fold the pinna forward, as in the conventional procedure.
- b) Enter the pre-op audiogram into the software.
- c) Normal CI surgical approach. A conventional round window or extended round window entry into the cochlea is prepared.
- d) Measure ECochG in response to a 500 Hz tone burst stimulus, at 110 dB SPL, during insertion of the CI electrode and after insertion of the CI electrode. Figure 2 schematically depicts the intraoperative set-up. Figure 3 shows the non-invasive surface electrode and earphone array used in ECochG. Figure 4 shows the enclosure box and monitoring screen.
 - i) For participants randomized to Arm 1 of the study, the surgeon will perform CI electrode insertion without ECochG feedback.
 - ii) For participants randomized to Arm 2 of the study, the surgeon will make insertion modifications as appropriate in response to ECochG feedback.

3) Initial CI Activation Visit (3-5 weeks after surgery)

- a) Audio Assessment
 - i) Unaided pure tone audiometry in the implanted and the unimplanted ear
 - ii) Bone-conduction thresholds when possible, depending on the patient's residual hearing status

- iii) For pediatric patients, unaided audiometric data may be collected as tolerated, across different visits, to accommodate the unique challenges of hearing assessment of young children.
- b) **Measure ECochG responses in clinic** (to coincide with audiology, +/- 1 week)
 - i) 125-2000 Hz (frequency scan)
 - ii) At an acoustic intensity level at or below their comfortable level through an insert earphone
 - iii) Directly through the CI
- c) Post-Op CT scan to identify CI electrode scalar location
 - i) Obtain scan within one month following surgery
 - ii) Patient identifiers removed from CT scan data and sent to collaborators in DICOM format for analysis (See Appendix 1).

4) Approximately 3 Month Visit

- a) Audio Assessment
 - i) Pure tone unaided audiology in the implanted and the unimplanted ear
 - ii) Bone-conduction thresholds when possible, depending on the patient's residual hearing status
- b) Measure ECochG responses in clinic (to coincide with audiology, +/- 1 week)
 - i) 125-2000 Hz (frequency scan)
 - ii) At an acoustic intensity level at or below their comfortable level through an insert earphone
 - iii) Directly through the CI

5) Approximately 12 Month Visit

- a) Audio Assessment

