In the operating room, a 500 Hz tone burst will be presented to the participant at a 110 dB SPL through an insert earphone in the external auditory canal. This acoustic stimulus will provoke movements of remaining inner and outer cochlear hair cells and evoke a response from the auditory nerve. Tone burst stimuli at 500 Hz have been shown to produce the largest amplitude ECochG response, therefore, will be used as the default stimulus here. The resulting cochlear potentials will be recorded using the recording electrode from the apical aspect of the CI electrode. By averaging the recorded signal synchronized with stimulus delivery, the responses can be reinforced while unsynchronized noise will average out. For a more detailed description of ECochG measurements, please see [10]. This utilization is consistent with indications covered under this FDA 510(k) clearance.

Intra-operative preparation

The insert earphone will be placed in the external ear canal after cerumen removal. The ear canal will be surgically prepared, followed by suctioning of prep fluid. Following the conventional technique, the measurement ear will be folded forward and taped. The surgery will proceed following the standard-of-care practice consisting of a cortical mastoidectomy, a facial recess (posterior tympanotomy), and preparation of intracochlear access via the round window or an extended round window approach. Before the CI electrode will be inserted, the headpiece will be connected to the implant, and the ECochG software will be triggered to begin the ECochG recordings. Figure 2 depicts a schematic of the measurement system setup. Figure 3 shows an example of the noninvasive surface electrode and earphone array. Figure 4 shows the monitor and unit through which the ECochG is observed and recorded.

To facilitate correlation of changes in ECochG potentials during CI electrode insertion and surgical events that ultimately relate to trauma within the cochlea, the surgeon will verbally indicate the progress of electrode insertion (e.g., “at the round window,” “at the first marker on the electrode,” “at the last marker on the electrode”), which will be recorded in the software by an assistant and synched with the ECochG signals.

Post-operative ECochG

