Scalar Dislocation: Preliminary data indicates that the current state of CI electrode dislocation from the scala tympani to the scala vestibuli is approximately 35% (or, a “successful” scala tympani position is achieved at a rate of 65%). For participants randomized to “ECochG audible signal on,” our expectation, driven by preliminary data, is to decrease the rate of scalar dislocation to approximately 15% (or, a “successful” scala tympani position rate of 85%). Setting the alpha error rate at 2.5%, a total sample size of 192 participants, or 96 participants in each of the two randomization groups, was determined using a Fischer exact test. If we permit a 5% error rate, the total sample size drops to 162 patients (81 randomized to audible signal “on”; 81 randomized to signal “off”). While these numbers of participants are higher than would be possible to achieve at our site alone in an average two-year period, through a coordinated effort to pool multi-center data, it will be easily achievable.

Secondary Planned Analysis

Electrode Type: As detailed above, once a participant is enrolled in the study, the surgeon will select which of two CI electrodes are most appropriate. A secondary analysis comparing scalar position and hearing preservation outcomes will be performed (i.e., four total between-group analyses) between the two electrode groups.

Pediatric Participants: This study will include both adult and pediatric participants. A secondary analysis comparing scalar position and hearing outcomes between adult and pediatric participants will be performed (again, four total between-group analyses).

Regression Analysis: To model the influence of “ECochG on” on the primary outcome measures in the context of participant age group and electrode choice, two regression analyses will be performed – one for the outcome measure of scalar position and one for hearing outcomes.

Hospital Effect Analysis: To determine if there is a meaningful difference in outcome measures across the different participating hospital settings, a secondary analysis will be performed as well.

Safeguarding of Protected Health Information (PHI)

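### The protocol does not say when on the day of surgery the surgeon learns the arm, so the cochlear entry route may be chosen with the arm known

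*Protocol*

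**What the plan says.** On masking, the Randomization section (under Participants) says that the arm "will be unknown to the investigators at the time of enrollment and to the participants themselves". For surgeons it says: "By necessity, surgeons themselves will be “unblinded” on the day of surgery". No time within the day is given, and no step withholds the arm until a particular point in the operation.

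On the order of events, Protocol timeline, 2) Day of surgery, step c reads: "A conventional round window or extended round window entry into the cochlea is prepared". ECochG measurement during insertion follows as step d. In Arm 1, "the surgeon will perform CI electrode insertion without ECochG feedback"; in Arm 2 the surgeon responds to it. Intra-operative preparation gives the same order. It ends the surgical approach with "preparation of intracochlear access via the round window or an extended round window approach" and continues: "Before the CI electrode will be inserted, the headpiece will be connected to the implant, and the ECochG software will be triggered". Under Arm 1, responses are recorded although the surgeon does not receive them, so recording takes place in both arms.

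On electrode type, Outcome Measures has the surgeon select it pre-operatively and the patient randomized afterwards. Protocol timeline, 1) Pre-Operative, step b also lists it before surgery.

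**The concern.** A surgeon who must react to a sound in one arm and works without it in the other cannot be masked during insertion. That necessity begins at insertion. Before it, the protocol intends the two arms to be treated alike, and nothing the surgeon does requires the arm.

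One discretionary choice falls in this interval: round window or extended round window entry. The protocol gives no rule for choosing and no instruction to record the choice before the arm is known. Randomization balances what precedes it; it cannot balance a decision taken afterwards with the arm known. If the mix of routes differed between arms, and if route has any bearing on scalar position or residual hearing, the comparison would no longer isolate the effect of hearing the signal. The planned regressions name age group and electrode choice as covariates, not entry route. A statistical analysis plan cannot repair this later, because masking in the operating room and the timing of a record are settled by the protocol.

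**Working it through.** **1. When is the arm needed?**

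| Step | Same in both arms? | Arm needed by surgeon? |
|---|---|---|
| Electrode type selected (pre-operative) | Yes | No; randomization follows |
| Earpiece placed, audiogram entered (2a, 2b) | Yes | No |
| Mastoidectomy, facial recess, cochlear entry (2c) | Intended to be | No |
| Headpiece connected, recording triggered | Yes, both arms recorded | From this point |
| Insertion (2d) | No | Yes |

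Because both arms are recorded, setting up the equipment need not reveal the arm. An assistant already enters insertion progress in the software (Intra-operative preparation).

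**2. The plan's own sample size.** Inputs from Power Analysis: dislocation 35% v 15%, alpha 2.5%, 96 per arm, Fisher exact test. Sidedness and power are not stated. Exact enumeration of the two-sided test gives power 0.807; at alpha 5% with 81 per arm it gives 0.802. Both stated sizes therefore reproduce at about 80% power, two-sided. Later disclosure changes none of these inputs.

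**3. Illustrative size. The inputs are assumptions, not document figures.** The protocol gives no dislocation rate by entry route. Let s be the share of the signal-on arm whose route changes because the arm is known, and d the difference in dislocation rate between routes. The shift is s × d. With s from 10% to 30% and d from 10 to 20 points, it runs from 0.10 × 10 = 1 point to 0.30 × 20 = 6 points, against the planned 35 − 15 = 20.

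Two-sided Fisher test, 96 per arm, p ≤ 0.025, exact enumeration:

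| Shift | No true effect, shift lowers signal-on rate: rejection rate | True 35% v 15%, shift raises signal-on rate: power |
|---|---|---|
| 0 | 35% v 35%: 0.017 | 35% v 15%: 0.807 |
| 1 point | 35% v 34%: 0.018 | 35% v 16%: 0.751 |
| 2 points | 35% v 33%: 0.022 | 35% v 17%: 0.688 |
| 3 points | 35% v 32%: 0.028 | 35% v 18%: 0.621 |
| 6 points | 35% v 29%: 0.068 | 35% v 21%: 0.415 |

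In the false-positive direction, shifts of 1 or 2 points stay under 2.5%, because Fisher's test is conservative. The 6.8% needs both assumptions at their upper end. Nothing in the documents says which direction, if either, applies.

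**4. What later disclosure cannot reach.** The Randomization section under Statistical Analysis fixes blocks of two at each institution, one participant per arm. Once the first allocation in a block is known, the second is certain. With complete blocks, that is up to 192 / 2 = 96 participants whose arm a surgeon aware of the preceding allocation could infer before the operation.

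**The case against.** The strongest reply is that the sentence is correct as it stands. Surgeons cannot be masked in this trial, and the wording also fits disclosure just before insertion. That stands. A reader might infer that surgeons know the arm all day, or that pre-insertion choices are in fact made with that knowledge. The text supports neither; it leaves the moment open.

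A reader might also infer that electrode choice is exposed. Secondary Planned Analysis says "once a participant is enrolled in the study, the surgeon will select which of two CI electrodes are most appropriate", and enrolment on the day of surgery is allowed. But enrolment is not randomization, and Outcome Measures puts the choice before randomization. The passages do not conflict. Electrode choice needs only a record made before disclosure.

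Third, the documents never link entry route to scalar position or hearing, and they describe the approach as standard care for everyone. This also stands. The bias is possible, not shown, and a surgeon without feedback might be the more cautious one, which would bias towards no difference.

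Finally, insertion vector and speed remain at the discretion of an unmasked surgeon. That exposure cannot be removed, because the intervention acts through it. It is no reason to leave the avoidable part open.

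**Conclusion.** The point holds in a limited form. The protocol does not state when the arm is disclosed within the day of surgery and does not withhold it until recording is triggered, the first point at which it is needed. The choice between two permitted entry routes is therefore open to knowledge of the arm.

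The size and direction of any bias are unknown. The figures above depend wholly on assumed shifts of 1 to 6 points and show only that the consequence could range from negligible to material. They are not an estimate. The planned sample size is unaffected. This is worth correcting because the correction is cheap, not because harm has been demonstrated.

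**What to change.** Amend the Randomization section to state that:

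- electrode type and entry route are recorded before the arm is disclosed;
- the assistant running the ECochG software discloses the arm to the surgeon when recording is triggered, immediately before insertion, and sets the audio on or off;
- any change of electrode or route after disclosure is logged with its reason.

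This leaves the choice of route with the surgeon and prescribes none. For full effect, replace the fixed blocks of two with varied block sizes that are not disclosed to the sites; otherwise a surgeon who knows the preceding allocation can still infer the next.

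The cost is a short protocol amendment and one extra step in the operating room, with no added staff, visits or participants. Changing the blocks means reissuing the unused part of each institution's schedule.

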The potential utility of ECochG during CI is illustrated by the following scenario: if the CI electrode touches the delicate structures of the cochlea (i.e., the basilar membrane or the spiral ligament) during insertion, the ECochG potentials become smaller in amplitude. With a real-time measurement system used during electrode insertion, decrease in ECochG potentials could be detected, and the surgeon could more purposely employ their modifications to insertion technique such as changing the insertion angle to avoid trauma or translocation.

Use of intra-cochlear electrodes for ECochG offers an additional capability of observing potentials post-operatively in the clinic. ECochG allows an objective method of monitoring hearing at regular intervals over the early post-operative period and may give insights into hearing outcomes.

Study Design

A prospective, randomized, multi-center controlled study design will be used in this study. The total study duration will be up to two years. This study will be conducted in agreement with the Internal Review Board (IRB). The study will be registered through Clinical Trials.gov (account created; registration pending IRB approval).

Outcome Measures

The post-operative outcome measures of this study will be (1) the CI electrode's scalar position as indicated by post-operative computed tomography (CT) and (2) post-operative hearing performance. Following the clinical convention, the surgeon will pre-operatively select the type of CI electrode (i.e., the MidScala electrode or the SlimJ electrode) that they would like to use during surgery. As detailed below, the patient will then be randomized to "audible ECochG signal off" or "audible ECochG signal on."

Hypotheses

The hypotheses of this study are that:

- (1) Changes in the ECochG signal observed during CI electrode insertion will correlate with insertion position outcomes as indicated by post-operative CT scan.
- (2) Participants randomized to "ECochG audible response on" will demonstrate a significantly lower rate of scalar dislocation compared to participants randomized to "ECochG audible response off."
- (3) Changes in the ECochG signal during CI electrode insertion will correlate with post-operative audiogram.
- (4) Post-operatively, changes in the ECochG *signal over time in clinic* will correlate with changes observed *over time* in post-operative audiograms.

Participants

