This condition is identical to the current standard-of-care for conventional CI surgery used worldwide. The surgeon will perform his or her electrode insertion without ECochG monitoring. Minute manipulations of the electrode are a normal part of conventional electrode insertion; manipulations such as redirecting the insertion vector or slowing down insertion speed will be made, as deemed necessary by the surgeon. A full electrode insertion will be performed, as appropriate. The ECochG responses will be recorded, but the surgeon will be blinded to this information during surgery.

Arm 2: Audible ECochG Response On

This condition will have the audible ECochG response on and available to the surgeon. In this condition, the surgeon perform a conventional electrode insertion while listening to the running ECochG signal for drop in amplitude (suggesting impending trauma). If no drop is detected, insertion will proceed to the full electrode length according to the standard-of-care. If an ECochG amplitude drop is observed, the surgeon will place this observation in its clinical context and evaluate insertion parameters, (i.e., insertion vector, insertion speed, etc.), customary practice with conventional CI surgery, but here

supplemented by the ECochG response. In the case of an ECochG amplitude drop that does not recover, the standard-of-care practice of achieving a full electrode insertion will be followed.

Protocol timeline

1) Pre-Operative (typically 1-30 days before surgery)

- a) Standard counselling regarding CI study; collect consent form for adults or assent form for pediatric participants; collect data release forms.
- b) The surgeon makes his or her CI electrode selection between two options: (1) the HiFocus SlimJ (lateral wall array) or (2) the HiFocus MidScala. Electrode selection is a normal component of conventional CI surgery. All CIs models to be utilized in this study are FDA-approved and will be used within their approved indications (Ultra MS: Model# CI-1600-04, FDA PMA Approval Number P960058/S117; Ultra Slim J: Model# CI-1600-05, FDA PMA Approval Number P960058/S121).
- c) Pure tone audiometry (standard-of-care pre-operative CI candidacy evaluation). In pediatric patients, for whom completion of pure tone audiometry may be difficult or unreliable, auditory brainstem response (ABR) testing can be used to supplement or estimate behavioural thresholds.
- d) Pre-operative CT scan (standard-of-care) for surgical planning.

2) Day of surgery

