Block randomization is statistical strategy to prevent unequal numbers of participants from being randomized to one arm vs the other (here, audible signal "on" versus audible signal "off"). For example, using a random number generator set to individually assign 100 participants to one of two groups, there is no assurance that an equal numbers of study participants would end up in the "audible signal on" group, resulting in an unbalanced overall sample, despite randomization of each participant.

Using a block approach, the total sample is divided into smaller blocks and randomization is performed within each block with the rule that the number of allocations is balanced within that block. In our study, although each institution will likely only contribute about 40 participants, we have designed a randomization schedule to allow for 100 participants to be run for each program. This sample of 100 was divided into 50 blocks of two participants; the two participants are randomized ensuring that one goes into the "signal off" group and one goes to the "signal on" group.

Power Analysis

To ensure that our study is appropriately powered to detect a significant difference in the primary outcomes measures, we performed a power analysis with the assistance of a biostatistician. Post-operative CT-based indication of scalar position is treated as a dichotomous variable (i.e., either in the scala tympani or in the scala vestibuli); post-operative hearing outcomes are treated as a continuous variable.

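### Fixed blocks of two, printed in the protocol, let the second arm of a pair be deduced once the first participant has been operated on, so concealment at enrollment is not secured

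*Protocol*

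**What the plan says.** - **Statistical Analysis, Randomization.** Each program has a list of 100 places: "This sample of 100 was divided into 50 blocks of two participants". One member of every pair goes to signal off and the other to signal on. Expected recruitment is smaller: "although each institution will likely only contribute about 40 participants".
- **Randomization (after Participants).** The lists are site-specific: "For each participating institution, an impartially designed randomization schedule has been drawn up". Concealment is claimed: "The arm to which participants are randomized will be unknown to the investigators at the time of enrollment". The surgeon is the exception: "By necessity, surgeons themselves will be" aware of the arm at the operation. In Arm 2 the surgeon listens to the signal, so this cannot be avoided.
- **Participants and Protocol timeline.** Candidates may join "at the time of their regular pre-operative clinic visit or on the day of surgery itself". The pre-operative step usually falls between 1 and 30 days ahead of surgery.
- **Study Design.** "The total study duration will be up to two years". The last visit is at about 12 months.
- **Electrode choice.** Outcome Measures puts it before randomization. Secondary Planned Analysis puts it after enrollment.

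The Protocol describes no varying block size and no other protection against deducing the next arm.

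**The concern.** With one fixed block size of two, the first arm of a pair reveals the second. The size is printed in a document that every site holds, and the site's surgeon learns each arm in the operating room. Enrollment is rolling, so the second member of a pair will often be approached after the first has been operated on. Anyone who knows the position on the list then knows the coming arm, and the concealment claim fails for that participant.

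Whether to enroll a candidate, when to do so, and which electrode to use could then respond to a known arm. That would bias the between-arm comparison of scalar dislocation. The planned regression includes age group and electrode choice and can adjust for those two. It cannot adjust for selection on unmeasured surgical difficulty.

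**Working it through.** **1. The plan's own figures.** 50 blocks x 2 = 100 places per site, as stated. The sample size also reproduces: 96 per arm, 35% against 15%, two-sided Fisher exact test at 2.5% gives 80.7% power. The Protocol does not state sidedness; the two-sided test is used below because it fits the stated number at about 80% power.

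**2. Ceiling.** In each pair the first arm is a coin toss and the second is fixed.
- Allocations determined: 1/2, that is 20 of 40 per site and 96 of 192 overall.
- Best-guess success: (0.5 + 1)/2 = 75%, against 50% under full concealment.

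**3. Share known under the Protocol's timing.** From the Protocol: about 40 per site, and surgery 1 to 30 days after the pre-operative visit. Assumed: random (Poisson) arrivals, a lag uniform over 1 to 30 days, a list position taken at enrollment, and accrual over 12 or 24 months.

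The first arm is known at the next enrollment if that enrollment comes after the first operation: f = E[exp(-rate x lag)] = (e^(-rate) - e^(-30 x rate)) / (29 x rate).
- 12 months: rate = 40/365 = 0.1096 per day (mean gap 9.1 days), f = (0.896 - 0.037)/3.178 = 0.270.
- 24 months: rate = 40/730 = 0.0548 per day (mean gap 18.3 days), f = (0.947 - 0.193)/1.589 = 0.474.

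Only second places can be deduced, so the share of all allocations is f/2.

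**4. Variations.** If a share q enrolls on the day of surgery, f becomes q + (1 - q) x f. The Protocol gives no value for q. At q = 0.25 the share of all allocations is 22.6% to 30.3%; at q = 0.5 it is 31.8% to 36.9%. If a site has two surgeons who do not share information and q = 0, simulation gives 6.5% and 12.0%.

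**5. Illustration of bias.** All inputs here are assumed: dislocation risk of 50% in harder and 20% in easier cases, mixed equally (average 35%, the Protocol's control rate); no true effect; and, when the arm is known, the share of harder cases moved 20 points down for signal on and up for signal off.

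A steered place changes risk by 0.20 x 30 = 6 points. Second places make up half of each arm, so the difference between arms is 2 x (1/2) x f x 6 = 6f points. The last column is the exact probability that the two-sided Fisher test at 2.5%, with 96 per arm, rejects in favour of signal on.

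| Scenario | f | Known, of 192 | Bias (points) | False benefit |
|---|---|---|---|---|
| No steering | – | – | 0 | 0.85% |
| 12 months, q = 0 | 0.270 | 26 (13.5%) | 1.62 | 1.57% |
| 24 months, q = 0 | 0.474 | 46 (23.7%) | 2.84 | 2.42% |
| 12 months, q = 0.5 | 0.635 | 61 (31.8%) | 3.81 | 3.33% |
| 24 months, q = 0.5 | 0.737 | 71 (36.9%) | 4.42 | 4.05% |
| Every second place known | 1 | 96 (50%) | 6.00 | 6.47% |

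A 10-point shift halves the bias; at q = 0 it gives 0.8 to 1.4 points and 1.2% to 1.5%.

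**6. Other block schemes.**

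| Scheme | Determined | Best guess right |
|---|---|---|
| Fixed 2 | 50% | 75% |
| Fixed 4, size known | 33% | 71% |
| Fixed 6, size known | 25% | 68% |
| Fixed 8, size known | 20% | 67% |
| Random 4/6/8 | 2.4% | 67.6% |

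The last row comes from 2000 simulated lists of 40, for an observer who knows the set of sizes and every earlier arm but not the order of the sizes.

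**The case against.** - **Accrual.** If the two-year limit includes the 12-month visit, accrual is at most about 12 months and only the lower figures apply (27% known, 26 of 192). This stands as a caution. The Protocol does not settle it, because the power section also speaks of recruitment over a typical two-year period.
- **When a list position is used.** The Protocol does not say. If it is taken later than enrollment, the known share rises, so the 14% to 24% is not firmly anchored in either direction.
- **Who knows what.** The Protocol speaks separately of investigators and surgeons, and the person enrolling must know both the list order and the previous arm. That limits exposure, but nothing keeps the two roles or their knowledge apart.
- **Electrode choice already precedes randomization** in one section. That order protects the choice only if the coming arm cannot be predicted, and another section places the choice after enrollment.
- **Size of the bias.** The risks and the shift are assumed. With no enrollment on the day of surgery, the 1.6 to 2.8 points are small beside the planned 20-point difference, and the false-benefit rate stays below 2.5%. The smallness is fair. The fairer yardstick, though, is the 0.85% without bias, or the 1.25% that a two-sided 2.5% test nominally allows in one direction.
- **Residual guessing.** With mixed block sizes the best guess is still right about 68% of the time, so the excess over chance falls only from 25 to about 18 points. This is correct: the gain is chiefly in certainty.

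None of this restores the concealment that the Protocol claims.

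**Conclusion.** The concern holds. That the second arm can be deduced follows from the Protocol's own text and needs no assumption beyond the first operation coming before the second enrollment and the list order being known. The ceiling of 96 of 192 is exact. The 26 to 46 of 192 rests on the arrival, lag and accrual assumptions, and the true figure could lie on either side. The bias and error rates are illustrations only; the document does not show that steering occurs. The sample size is not affected. A statistical analysis plan could not cure the problem, because the lists are already drawn up, the block size is disclosed, and analysis cannot restore concealment afterwards. This should be fixed, though it does not by itself invalidate the design.

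**What to change.** 1. Have the biostatistician regenerate the unused part of each site's list with block sizes that vary at random, for example 4, 6 and 8.
2. Remove the block sizes from the Protocol and keep them in a document withheld from the sites.
3. Release each allocation only after enrollment and electrode choice have been recorded, and give the same order of events in Outcome Measures and Secondary Planned Analysis.

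The cost is the new lists and a short amendment. Places already used cannot be changed. The downsides are a possible imbalance of a few participants per site and a next arm that can still be guessed better than chance.

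### Does the protocol claim power for hearing as well as scalar position when only the dislocation calculation is reported?

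*Protocol*

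**What the plan says.** Under Participants, the protocol sets the total at 192 and adds: "This sample size was determined by a power analysis, detailed below in Statistical Analysis". The Power Analysis section states that "we performed a power analysis with the assistance of a biostatistician" so that the study is "appropriately powered to detect a significant difference in the primary outcomes measures". It then classifies scalar position as dichotomous and says that "post-operative hearing outcomes are treated as a continuous variable".

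One calculation follows, under Scalar Dislocation. It takes 35% dislocation with the audible signal off, 15% with it on, and Fisher's exact test: "Setting the alpha error rate at 2.5%, a total sample size of 192 participants, or 96 participants in each of the two randomization groups". An alternative is given as well: "If we permit a 5% error rate, the total sample size drops to 162 patients".

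The Regression Analysis paragraph shows that both outcomes count as primary. It models the effect of the audible signal "on the primary outcome measures in the context of participant age group and electrode choice", with two models, "one for the outcome measure of scalar position and one for hearing outcomes".

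**The concern.** The power claim is plural and the calculation is singular. For hearing, the section gives the type of variable and nothing else: no difference, standard deviation, test, alpha, power or sample size. The Hypotheses section does not fill the gap. Its second hypothesis is the between-arm comparison of dislocation, while the two that concern audiograms are correlations with the ECochG signal. The protocol also names no single hearing quantity, since audiometry is planned at three post-operative visits and the thresholds are to be reported frequency by frequency.

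Two things would be at stake. A null hearing result might be read as coming from a trial sized to find a difference. And 192 − 162 = 30 participants (30/192 = 15.6%) depend on choosing 2.5% over 5%, with no reason stated. If the 2.5% were merely the one-sided form of an ordinary 5% test, the trial would be larger than its own assumptions require.

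**Working it through.** **Inputs from the protocol (Scalar Dislocation; Randomization).** p1 = 0.35, p2 = 0.15, 1:1 allocation, Fisher's exact test; 96 per arm at alpha 2.5%, 81 per arm at alpha 5%. Sidedness and target power are not stated, so both sides were tried.

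**Step 1: reproduce the stated sizes.** Exact power is the sum, over all pairs (x1, x2) for which Fisher's p ≤ alpha, of Bin(x1; n, 0.35) × Bin(x2; n, 0.15).

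| Test | Alpha | Power at stated n | Smallest n per arm for 80% | Smallest n per arm for 90% |
|---|---|---|---|---|
| Two-sided | 2.5% | 80.7% (n = 96) | 95 | 122 |
| Two-sided | 5% | 80.2% (n = 81) | 81 | 104 |
| One-sided | 2.5% | 87.5% (n = 96) | 81 | 104 |
| One-sided | 5% | 87.8% (n = 81) | 65 | 87 |

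The stated pair (96, 81) matches two-sided testing at 80% power, to within one participant per arm. A one-sided reading gives (81, 65) at 80% and (104, 87) at 90%, and neither fits.

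**Step 2: cross-check with the normal approximation, two-sided, 80% power.** The mean proportion is 0.25.

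n = [z(1−α/2)·√(2 × 0.25 × 0.75) + 0.8416·√(0.35 × 0.65 + 0.15 × 0.85)]² / 0.20²

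- Alpha 2.5%: (2.2414 × 0.6124 + 0.8416 × 0.5958)² / 0.04 = 87.8, so 88; with continuity correction, 98.
- Alpha 5%: (1.9600 × 0.6124 + 0.8416 × 0.5958)² / 0.04 = 72.4, so 73; with continuity correction, 83.

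The corrected values lie within 3% of 96 and 81.

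**Step 3: where 2.5% could come from.** Step 1 shows that it is a two-sided level, not one tail of a 5% test. It equals 0.05/2, which suits a Bonferroni split over two primary outcomes: the sum is 5%, or 1 − 0.975² = 4.94% if the tests are independent. This is inference, because the protocol does not say so.

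**Step 4: what 96 per arm offers for hearing.** Every input here except n is assumed: 80% power, complete hearing data, no adjustment for the pre-operative threshold. The detectable difference in SD units is (z(1−α/2) + 0.8416) × √(2/96), with √(2/96) = 0.1443.

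- Alpha 2.5%: (2.2414 + 0.8416) × 0.1443 = 0.445.
- Alpha 5%: (1.9600 + 0.8416) × 0.1443 = 0.404.

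At 2.5%, power would be 44% for a true difference of 0.3 SD, 70% for 0.4 SD and 89% for 0.5 SD. Adjustment for the pre-operative threshold would improve these figures and missing data would worsen them. With no difference or SD in the protocol, nothing here shows 192 to be too few.

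**The case for a change.** The strongest case for acting is that the protocol itself makes the claim. It ties its sample size to a power analysis, directs the reader to its own Statistical Analysis section, and there supports only half of what it says. On that view this is not something deferred to another document, and limiting one sentence would cost no patients.

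The textual part of that stands: the sentence is wider than the calculation under it. The rest is weaker. A hearing calculation that needed fewer than 192 may exist and not be printed, since the section does say how hearing was treated. The frequency, the visit, the between-arm hearing test and the reason for the alpha level are commonly fixed in a statistical analysis plan, which may exist and is not shown. The absence of a between-arm hearing hypothesis is partly met by the planned regression of hearing on the audible signal.

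One could count eight reported frequencies at three visits as 24 candidate endpoints, but the protocol does not define them that way. The list under Pure tone and bone-conduction audiology is a reporting rule, limited to patients whose pre-operative low-frequency average is below 80 dB HL. The same section measures eleven frequencies.

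Nor would a narrower sentence do much to protect the reading of a null hearing result. That rests on the confidence interval. With 96 per arm and the assumptions of Step 4, the 95% half-width would be 1.9600 × 0.1443 = 0.28 SD, whatever the power section says.

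**Conclusion.** No change to the plan follows. The sample size is correctly derived for the comparison that the second hypothesis states: 192 and 162 both reproduce as two-sided Fisher tests with about 81% and 80% power. The unexplained 2.5% is stricter than 5%, the protocol openly shows the size at each level, and the choice does no harm to validity; its cost is 30 participants. For hearing, the protocol states no power figure that could be wrong, and the documents do not show that 192 is inadequate. The 0.45 SD and 0.40 SD figures rest on assumed power and complete data, and are too speculative to serve as protocol text.

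What remains is loose wording and unreported detail: the sidedness, the target power, the reason for 2.5%, and the basis for hearing, if there was one. An analyst can recover the first two from the stated sizes, and the others can properly sit in the analysis plan. Supplying them would alter neither the design, the analysis nor any conclusion. When results are reported, it is enough to say that the only sample-size calculation in the protocol concerns dislocation, and to let the interval carry the hearing result.
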